2.7 Safety analyses

Safety analyses will be summarized for the safety set and by dose cohort (adults with sabatolimab 400 mg, adults with sabatolimab 800 mg, adults with azacitidine & sabatolimab combination, adolescents with sabatolimab monotherapy).

Safety summaries (tables) include only data from the on-treatment period with the exception of baseline data which will also be summarized where appropriate (e.g. change from baseline summaries). In addition, a separate summary for death including on treatment and post treatment deaths will be provided. In particular, summary tables for adverse events (AEs) will summarize only on-treatment events, with a start date during the on-treatment period (treatment-emergent AEs). Listings will be also provided.

The overall observation period will be divided into three mutually exclusive segments:

- 1. Pre-treatment period: from day of participant's informed consent to the day before the first administration of study treatment
- 2. On-treatment period: from the date of the first administration of study treatment to 30 days after the date of the last administration of study treatment
- 3. Post-treatment period: any observation starting at day 31 after the last administration of study treatment

An overall safety period will be defined from date of the first administration of study treatment to 150 days after the last dose of sabatolimab.

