Part 2 will assess efficacy as well as safety, PK, and MRD status when sabatolimab is administered at the recommended dose for expansion determined in Part 1 as monotherapy and/or in combination with azacitidine. Part 2 will enroll a total of approximately 13 participants in the monotherapy expansion [to obtain a total of 25 participants from the combined Safety Run-in (Cohort 2) and monotherapy expansion cohort (Cohort 4)]; and 20 participants in the combination cohort (Cohort 3). Participants will be randomized to one of these two cohorts in Part 2 - combination cohort (Cohort 3) or monotherapy expansion cohort (Cohort 4) - and the randomization ratio will depend on the number of participants from the Safety-Run in part (Part 1) already treated with sabatolimab at the selected dose level for expansion (See Section 6.3.2).

In the monotherapy expansion cohort (Cohort 4), sabatolimab will be administered as a single agent on Day 1 (Q4W) of every 28-day cycle.

In the combination cohort (Cohort 3) of sabatolimab with azacitidine, sabatolimab will be administered on Day 5 (+3 days) of every 28-day cycle IV on a Q4W regimen.

[figure not shown]
Azacitidine will be administered IV or SC at 50 mg/m² on Days 1 to 5 for 5 days per cycle. In the combination cohort (Cohort 3), participants unable to tolerate one of the study drugs may continue on study receiving only the tolerated study drug.

In addition, based on Part 1 Safety Run-in results, an additional cohort of 6 adolescent participants (Cohort 5) will be opened (if no unacceptable rate of toxicities is observed in adults) to include participants who are 12 years or older but less than 18 years old and meet eligibility for this study. This cohort will be conducted in aHSCT site(s) that treat participants at this age group.

The decision to open the combination cohort (Cohort 3) and the adolescent cohort (Cohort 5) will be based principally on safety data obtained in Part 1. The decision to open the sabatolimab monotherapy expansion cohort (Cohort 4) will be based on an overall assessment of available safety, preliminary response assessment, PK, and MRD assessments.

Throughout the study, the decision whether or when to open an additional cohort(s) will be based on the overall safety, PK, tolerability, and preliminary response assessment.

Figure 3-1 Study design

Page 34 of 153 Protocol No. CMBG453F12201

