Study treatment will be administered for up to a maximum of 24 cycles or until a participant experiences hematologic relapse (bone marrow blasts ≥5%; or reappearance of blasts in the blood; or development of extramedullary disease) as defined by ELN 2017 (Döhner et al 2017); or unacceptable toxicity, whichever is earlier. For participants who achieve negative MRD and maintain MRD negativity for 12 consecutive cycles, study treatment (sabatolimab monotherapy or sabatolimab in combination with azacitidine) may be discontinued earlier at investigator's discretion.

In each cohort, response status will be evaluated by standard hematologic/morphologic criteria per investigator's assessment after each cycle up to Cycle 3, then after every 3 cycles of study treatment up to cycle 12, and then after every 6 cycles for up to a total of 24 cycles (post cycle 1, 2, 3, 6, 9, 12, 18, 24).

For participants with MRD+ centrally assessed at baseline (defined as at time of enrollment prior to starting treatment), MRD status will be evaluated by Novartis central laboratory at the same schedule as the hematologic/morphologic disease assessment after cycles 1, 2 and 3 and then after every 3 cycles of study treatment up to cycle 12, and then after every 6 cycles for up to a total of 24 cycles (post cycle 1, 2, 3, 6, 9, 12, 18, 24). In addition, MRD status will be assessed locally at the same schedule as the hematologic/morphologic disease assessment after cycles 1, 2 and 3 and then after every 3 cycles of study treatment up to cycle 12, and then after every 6 cycles for up to a total of 24 cycles (post cycle 1, 2, 3, 6, 9, 12, 18, 24).

After completion of the treatment period, all participants will enter post-treatment followup until hematologic relapse or start of new therapy.

After the end of study treatment, all participants must be followed for adverse events (AEs) for 150 days following the last dose of sabatolimab, or 30 days following the last dose of azacitidine, whichever is later. All participants who discontinued study treatment while in remission with absence of hematologic relapse will enter a long-term follow-up for efficacy as described in the study flow diagram below (Figure 3-2) and outlined in Section 9.1.

[figure not shown]
^{*} Criteria to proceed with sabatolimab dose increase or Go/No Go for Cohort 2: based on DLTs during the first 2 cycles of study treatment in Cohort 1.

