If the study treatment (sabatolimab + azacitidine) is interrupted for toxicities other than GvHD and the start of the subsequent study treatment cycle is delayed for more than 28 consecutive days from the intended start date of cycle (Day 29 of the previous cycle) the participant should be discontinued from study treatment. For permanent discontinuation of study treatment due to acute and/or chronic GvHD, refer to Table 6-4.

Permanent discontinuation of only one component sabatolimab (or azacitidine - Combination cohort)

If **one component only** of the study treatment (azacitidine or sabatolimab) is discontinued for toxicities (other than GvHD), then the treatment may continue with the other component of study treatment alone (sabatolimab alone or azacitidine alone) as long as the participant benefits per investigator's judgement.

These dose changes must be recorded on the appropriate CRF.

^{**}Per investigator judgement

Table 6-4 Criteria for dose interruption, re-initiation and discontinuation of study treatment due to GvHD

	y treatment due to G	T	Diagontino ()				
	Interrupt study treatment [£] (sabatoli mab monotherapy or in combination with azacitidine)	Resume study treatment (sabatolimab monotherapy or in combination with azacitidine)	Discontinue study treatment permanently (sabatolimab monotherapy or in combination with azacitidine)				
Acute GvHD (aGvHD)	New onset grade II requiring systemic therapy New onset grade III Baseline grade I or II worsening to grade III III III III III III III II	 If aGvHD improved to ≤ grade I or to baseline prior to starting study treatment within ≤ 8 weeks of observation from onset or exacerbation of aGvHD The following are allowed at time of resumption of study treatment: Topical, nonabsorbable or inhaled steroids Systemic doses of steroids ≤ 10 mg prednisone or equivalent Tacrolimus with trough levels <5 ng/mL OR CSA with trough levels <200 ng/mL (indicating continuous IST taper) 	 Grade IV aGvHD Recurrence or exacerbation of aGvHD to ≥ grade III after resuming study treatment Steroid-refractory aGvHD No improvement to ≤ grade I or to baseline prior to starting study treatment after 8 weeks of observation from onset or exacerbation of aGvHD 				

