- Dose not changed
- Dose reduced/increased
- Drug interrupted/withdrawn
- 6. its outcome

If the event worsens the event should be reported a second time in the CRF noting the start date when the event worsens in toxicity.

For grade 3 and 4 adverse events only, if improvement to a lower grade is determined a new entry for this event should be reported in the CRF noting the start date when the event improved from having been Grade 3 or Grade 4.

Conditions that were already present at the time of informed consent should be recorded in medical history of the participant.

Adverse event monitoring should be continued for at least

150 days after the last administration of sabatolimab, or 30 days after the last administration of azacitidine, whichever is later.

Page **107** of **153** Protocol No. CMBG453F12201

• Until the start of a new post treatment antineoplastic medication if sooner than the 150 days mentioned above. If a participant starts post treatment antineoplastic medication, then only adverse events suspected to be related to study treatment should be collected, up to 150 days after discontinuation of sabatolimab.

Adverse events (including lab abnormalities that constitute AEs) should be described using a diagnosis whenever possible, rather than individual underlying signs and symptoms. When a clear diagnosis cannot be identified, each sign or symptom should be reported as separate adverse event.

Once an adverse event is detected, it must be followed until its resolution or until it is judged to be permanent (e.g., continuing at the end of the study), and assessment must be made at each visit (or more frequently, if necessary) of any changes in severity, the suspected relationship to the interventions required to treat it, and the outcome.

Disease hematologic relapse / progression (including fatal outcomes), if documented by use of appropriate method [for example, as per ELN 2017 (Döhner et al 2017)], should not be reported as an adverse event. Adverse events separate from the disease hematologic relapse / progression (i.e., deep vein thrombosis at the time of hematologic relapse / progression or hemoptysis concurrent with finding of disease hematologic relapse / progression) will be reported as per usual guidelines used for such events with proper attribution regarding relatedness to the drug.

Information about adverse drug reactions for the investigational drug can be found in the Investigator's Brochure (IB).

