10.1.3 SAE reporting

To ensure participant safety, every SAE, regardless of causality, occurring after the participant has provided informed consent and until the end of the safety follow-up period (Section 9.1.1.1 must be reported to Novartis safety immediately, without undue delay, under no circumstances later than within 24 hours of learning of its occurrence. Detailed instructions regarding the submission process and requirements are to be found in the investigator folder provided to each site. Information about all SAEs is collected and recorded on the Serious Adverse Event Report Form; all applicable sections of the form must be completed in order to provide a clinically thorough report.

SAE reporting timeframes:

1. Screen Failures (e.g., a participant who is screened but is not treated or randomized): All SAEs occurring after the participant has provided informed consent until the time the participant is deemed a Screen Failure must be reported to Novartis.

2. Treated participants (including randomized participants in the Randomized Part): SAEs collected between time participant signs ICF until 30 days after the participant has discontinued or stopped azacitidine or 150 days after stopping sabatolimab, whichever is later. If a participant starts post treatment antineoplastic medication, then only SAEs suspected to be related to study treatment should be collected, up to 150 days or beyond after discontinuation of sabatolimab.

All follow-up information for the SAE including information on complications, progression of the initial SAE and recurrent episodes must be reported as follow-up to the original episode within 24 hours of the investigator receiving the follow-up information. A SAE occurring at a different time interval or otherwise considered completely unrelated to a previously reported one must be reported separately as a new event.

If the SAE is not previously documented in the Investigator's Brochure or Package Insert (new occurrence) and is thought to be related to the study treatment, a Chief Medical Office & patient Safety (CMO & PS) Department associate may urgently require further information from the investigator for health authority reporting. Novartis may need to issue an Investigator Notification (IN) to inform all investigators involved in any study with the same study treatment that this SAE has been reported.

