12.5.2 Safety endpoints

For all safety analyses, the safety set will be used. All listings and tables will be presented by dose cohort.

Safety summaries (tables, figures) include only data from the on-treatment period with the exception of baseline data which will also be summarized where appropriate (e.g. change from baseline summaries). In addition, a separate summary for death including on treatment and post treatment deaths will be provided. In particular, summary tables for adverse events (AEs) will summarize only on-treatment events, with a start date during the on-treatment period (treatment-emergent AEs).

The overall observation period will be divided into three mutually exclusive segments:

- 1. Pre-treatment period: from day of participant's informed consent to the day before first dose of study treatment
- 2. On-treatment period: from day of first dose of study treatment to 30 days after last dose of study treatment
- 3. Post-treatment period: starting at day 31 after last dose of study treatment.

An overall safety period will be defined from date of first administration of study treatment to 150 days after the last dose of sabatolimab.

Adverse events

Summary tables for adverse events (AEs) will include only AEs that started or worsened during the on-treatment period. The number (and percentage) of participants with treatment emergent adverse events will be summarized by primary system organ class, preferred term and maximum severity.

Separate summaries will be provided for study medication related adverse events, death, serious adverse events, other significant adverse events leading to discontinuation, and adverse events leading to dose adjustment.

Separate summaries will be provided for:

- treatment emergent grade III or grade IV acute GvHD
- treatment emergent moderate to severe chronic GvHD
- treatment-emergent ≥ grade 3 immune-related adverse events not attributed to GvHD

Serious adverse events and non-serious adverse events will be tabulated. All deaths (on-treatment and post-treatment) will be summarized.

In addition, all AEs and SAEs which started during the overall safety period will be summarized. All reported AEs will be listed and those that started during the pre-treatment, overall safety period and post-treatment period will be flagged.

Vital signs

All vital signs abnormalities will be summarized by visit.

Clinical laboratory evaluations

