2.2 Analysis sets

For the safety review meetings, the analysis sets defined below will be restricted to the population enrolled in the safety run-in part and participants will be analyzed according to the dose regimen they have been assigned to: sabatolimab 400 mg Q4W for the first cohort and sabatolimab 800 mg Q4W for the second cohort. At the time of the second Safety Review meeting to assess the overtoxicity risk for the second cohort (800 mg Q4W dose level), the available data from the first cohort (400 mg Q4W dose level) will also be displayed.

For the final analysis, the analysis sets defined below will include participants from both the safety run-in and the expansion parts. Participants will be analyzed according to the study treatment and the sabatolimab dose regimen they have been assigned to, as well as by the age group (adults versus adolescent). Thus, results will be presented by considering 4 dose cohorts:

- Adults with sabatolimab 400 mg (Cohort 1 + Cohort 4 if the RDE is 400 mg Q4W)
- Adults with sabatolimab 800 mg (Cohort 2 + Cohort 4 if the RDE is 800 mg Q4W)
- Adults with azacitidine & sabatolimab combination (Cohort 3)
- Adolescents with sabatolimab monotherapy (Cohort 5)

Full Analysis Set

The Full Analysis Set (FAS) comprises all participants who received at least one dose of any component of the study treatment (i.e. at least one dose of sabatolimab or at least one dose of azacitidine).

Safety Set

The Safety Set includes all participants from the FAS.

Dose-Determining Set

The Dose-Determining Set (DDS) includes all participants from the FAS enrolled in the safety run-in part and in the adolescent cohort (Cohort 5) who met the minimum exposure criterion described in the protocol Section 12.1 and had sufficient safety evaluations, or experienced a dose limiting toxicity (DLT) between Cycle 1 Day 1 (first dose of sabatolimab) and the end of

Novartis	Confidential	Page 17 of 35
SAP – Amendment 1		CMBG453F12201

Cycle 2 (both inclusive). Details on the definition of dose limiting toxicities (DLT) are presented in study protocol Table 6-2. A participant will be considered evaluable for DLT if:

- Participant has received 2 infusions of sabatolimab at the assigned dose level in Q4W dosing regimen, and participant has had safety assessments for a minimum period of 2 cycles (from Cycle 1 Day 1 to the end of Cycle 2), or

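### Cohort 3: the overall safety period has no azacitidine term, and the dose-intensity duration for Day 5 sabatolimab runs four days past the planned cycle end (minor; descriptive tables only)

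*SAP*

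**What the plan says.** **Safety window.** SAP 2.7 has two relevant periods. The overall one: "overall safety period will be defined from date of the first administration of study treatment to 150 days after the last dose of sabatolimab". The on-treatment one is worded in Protocol 12.5.2 as "On-treatment period: from day of first dose of study treatment to 30 days after last dose of study treatment" and carried into SAP 2.7. SAP 5.1 makes the last dose of study treatment the last non-zero dose of either component. SAP 2.7.1 plans AE and SAE tables by system organ class and preferred term on the overall period, next to the on-treatment tables.

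Collection follows a different rule. Protocol Section 3 follows participants for AEs for "150 days following the last dose of sabatolimab, or 30 days following the last dose of azacitidine, whichever is later". Protocol 10.1.1 repeats this ("150 days after the last administration of sabatolimab, or 30 days after the last administration of azacitidine, whichever is later"), and Protocol 10.1.3 collects SAEs "until 30 days after the participant has discontinued or stopped azacitidine or 150 days after stopping sabatolimab, whichever is later".

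Azacitidine alone is foreseen. Protocol Section 3 says that in Cohort 3 "participants unable to tolerate one of the study drugs may continue on study receiving only the tolerated study drug". Protocol 6.5.4 says that if one component is stopped for toxicity other than GvHD "then the treatment may continue with the other component of study treatment alone (sabatolimab alone or azacitidine alone"). The Full Analysis Set, and so the Safety Set, admits anyone with "at least one dose of sabatolimab or at least one dose of azacitidine" (SAP 2.2).

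**Dose intensity.** SAP 2.4.1 fixes planned sabatolimab intensity at 400 or 800 mg per 28 days. Its worked example gives a relative dose intensity (RDI) of 0.75 for an average of 600 mg against 800 mg planned. SAP 5.1 sets last exposure at last dose + 27 days for sabatolimab, whatever the cohort, and + 23 days for azacitidine. The dose-intensity duration runs from the first dose of the combination to the date of last exposure, plus one day, with no truncation at death or last contact.

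**The concern.** A window called overall should contain the on-treatment window, and its end should match the period in which events are collected. Here the start is tied to either drug but the end to sabatolimab only. For a participant who stays on azacitidine alone long enough, the overall-period AE and SAE tables would omit events that the on-treatment tables show. A reader comparing the two would find the wider-sounding table with the smaller count.

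The dose-intensity rule has a related fault. The 27-day offset suits a Day 1 dose. In Cohort 3 sabatolimab is given on Day 5 while the clock starts with azacitidine on Day 1. A participant dosed exactly as planned would be reported as under-dosed, most visibly after short exposure, and Cohort 3 would look less compliant than monotherapy for no clinical reason.

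**Working it through.** **Inputs.** 28-day cycles, at most 24 (Protocol 6.1.5). Cohort 3 receives azacitidine on Days 1–5 and sabatolimab on Day 5, with a ±3-day window but not before Day 5 in Cycle 1 (Protocol 6.1.1). Period ends are from SAP 2.7; offsets and start date from SAP 5.1; planned intensity and the 0.75 example from SAP 2.4.1.

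**1. Overall safety period.** Let the last sabatolimab dose be on Day 5 of a cycle, and the last azacitidine dose on Day 5 of the cycle k later. The doses are 28k days apart. Counted from the last sabatolimab dose, the on-treatment period ends at day 28k + 30 and the overall period at day 150.

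Shortfall = 28k + 30 − 150 = 28k − 120.

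| Azacitidine-only cycles k | On-treatment end (day) | Shortfall (days) |
|---|---|---|
| 4 | 142 | none (8 to spare) |
| 5 | 170 | 20 |
| 6 | 198 | 48 |

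If the last sabatolimab dose falls on Day d, the shortfall is 28k − 115 − d. Over Days 2 to 8 it is 23 to 17 days at k = 5, with 5 to 11 days to spare at k = 4. The five-cycle threshold holds across the window.

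For a participant with azacitidine only, there is no last sabatolimab dose from which to count, so the end date is undefined.

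**2. The SAP's own RDI example.** For Day 1 monotherapy over n cycles:

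- Duration = [28(n − 1) + 1 + 27] − 1 + 1 = 28n.
- RDI = (600n / 28n) / (800 / 28) = 0.75 for every n. The example reproduces.

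Azacitidine with its own offset also works: [28(n − 1) + 5 + 23] − 1 + 1 = 28n.

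**3. Sabatolimab in Cohort 3.** Day 5 + 27 = Day 32.

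- Duration = [28(n − 1) + 5 + 27] − 1 + 1 = 28n + 4.
- RDI for dosing as planned = 28n / (28n + 4).

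| n | Duration (days) | RDI, full dose | RDI, 600 of 800 mg |
|---|---|---|---|
| 1 | 32 | 28/32 = 0.875 | 0.656 |
| 6 | 172 | 168/172 = 0.977 | 0.733 |
| 24 | 676 | 672/676 = 0.994 | 0.746 |

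The intended values are 1.000 and 0.75 in every row.

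**4. After the changes.** Ending the overall period at the later of day 150 and day 28k + 30 leaves no shortfall for any k. Ending the dose-intensity duration on planned Day 28 gives 28n days, and so 1.000 and 0.75 for every n.

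**The case against.** Several points on the other side stand.

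- **Nothing is lost from the report.** The on-treatment tables and the AE listing still hold every event missing from the overall-period tables. A reader might infer that safety data disappear; they do not. Nor does any passage state that the two sets of tables must be nested. That expectation comes from the name and from the collection window.
- **The SAP follows the protocol here.** The overall period is taken from Protocol 12.5.2, so the conflict lies within the protocol too, and a SAP-only correction would be an unrecorded departure.
- **The 0.75 example is not contradicted outright.** It names no cohort and reproduces for Day 1 dosing. SAP 2.4.1 also defines planned intensity in words, as planned cumulative dose over the same duration; on that definition the duration cancels and RDI is 0.75 in Cohort 3 as well. It fails only with the explicit per-28-day figure and Day 5 dosing.
- **Truncation.** A reader might infer that RDI could exceed 1 when a participant dies mid-cycle, because the last-exposure dates are capped at death. SAP 5.1 expressly says that the dose-intensity duration is not so capped. What remains is loose wording: the formula names a date that is defined elsewhere with a cap.
- **Last cycle.** A reader might also infer that the SAP leaves open whether the last cycle is set per drug. It does not: SAP 5.1 sets it by the last non-zero dose of either component.
- **Cycle end.** SAP 5.1 does add a parenthesis allowing the end date to be Day 28 or beyond, but its stated definition is planned Day 28.

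The study also stopped early with a reduced report. That limits the consequence. But SAP Table 1-1 keeps the AE and SAE endpoint for the final report, and SAP 2.4.1 and 2.7.1 keep the outputs discussed here.

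**Conclusion.** Both rules are wrong as written, and the point is minor. It touches descriptive safety and exposure tables for Cohort 3 only; no primary endpoint or decision rule changes.

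The safety-window fault needs at least five azacitidine-only cycles after the last sabatolimab dose, or no sabatolimab at all. The dose-intensity fault applies to every Cohort 3 participant whose last sabatolimab dose is on Day 5, if the per-28-day figure is used. It is a constant four days: 12.5% of RDI at one cycle and 0.6% at 24. The figures assume cycles that start on schedule and azacitidine ending on Day 5. The documents do not give the number treated in Cohort 3, so the number affected is unknown and possibly zero.

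**What to change.** 1. In SAP 2.7, end the overall safety period at the later of last sabatolimab + 150 days and last azacitidine + 30 days, using whichever drugs the participant received. Record this in SAP Section 4 as a departure from Protocol 12.5.2; that section currently declares none.
2. In the dose-intensity formula of SAP 5.1, replace the date of last exposure with the SAP's own untruncated end date of the last cycle initiated, stated as planned Day 28. This also removes the clash with the no-truncation instruction. The capped last-exposure dates then serve duration of exposure only.
3. Keep the existing rule that either component sets the last cycle, or change it openly. It matters when azacitidine continues alone: with full sabatolimab dosing to cycle 6 and azacitidine to cycle 12, sabatolimab RDI is 168/336 = 0.500 under the existing rule and 168/168 = 1.000 with a per-drug last cycle. If the sponsor wants the latter, the definition in SAP 5.1 must say so.

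The cost is SAP wording, one entry in Section 4, minor programming, and a rerun of any affected Cohort 3 table already produced. No new data, visits or participants are needed.
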